9.4.1.1. Participant Disposition

A description of participant disposition will be provided, including a summary of the number and percentage of participants entered into the study, enrolled in the study, and treated, as well as number and percentage of participants completing the study (participants who receive at least 1 dose of study drug and have at least 1 postbaseline assessment), or discontinuing (overall and by reason for discontinuation). A summary of important protocol deviations will be provided.

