DSAD discontinuation rate has been higher than expected. The screening and enrollment numbers require increasing in order to reach the objective of the study.

Section Number and Name	Description of Change	Brief Rationale
Section 1.1 Synopsis	Increased number of patients enrolled	Number of patients required increasing to ensure the objective of the study is met
Section 5.2 Exclusion Criteria	Exclusion Criterion 12, added HS wording	Clarification of prohibited concomitant therapy
	Exclusion Criterion 16, the sites should use the 14 day/baseline (randomization) visit timing, not relative to the screening visit	Clarification of prohibited concomitant therapy
	Exclusion Criterion 35, hemoglobin level corrected to 90.0 g/L	Error correction
Section 6.5.1 Washout Period Before Enrollment	Added HS wording	Clarification of prohibited concomitant therapy
Section 6.5.4 Prohibited Concomitant Therapy	Added HS wording	Clarification of prohibited concomitant therapy rules
Section 8.1.1.2 Modified Sartorius Score (mSS)	Lesion distance corrected	Error correction
Section 8.1.6 Patient's Global Impression of Severity – 7 Days (Hidradenitis Suppurativa)	Clarified scoring system	Changed to match Patient's Global Impression of Severity form

Removed "at or" wording before the age of 40 years	To clarify that in reference it is <40
the age of 40 years	and not <=40
Number of patients enrolled increased	Number of patients required increasing to ensure the objective of the study is met
Electronic data collection is not occurring Correction of SAE reporting	Correction
N ir E	Tumber of patients enrolled nereased lectronic data collection is not

Table of Contents

1.	Protocol Summary	8
1.1.	Synopsis	
1.2.	Schema	
1.3.	Schedule of Activities (SoA)	11
2.	Introduction	24
2.1.	Study Rationale	24
2.2.	Background	24
2.3.	Benefit/Risk Assessment	24
3.	Objectives and Endpoints	26
4.	Study Design	27
4.1.	Overall Design.	27
4.2.	Scientific Rationale for Study Design	27
4.2.1.	Participant Input into Design	28
4.3.	Justification for Dose	28
4.4.	End-of-Study Definition	29
5.	Study Population	30
5.1.	Inclusion Criteria	30
5.2.	Exclusion Criteria	31
5.3.	Lifestyle Considerations	35
5.4.	Screen Failures	35
5.4.1.	Allowed Retesting of Screening Investigations	35
5.4.2.	Rescreening of Individuals Who Failed Screening	35
6.	Study Intervention	37
6.1.	Study Interventions Administered	
6.2.	Preparation/Handling/Storage/Accountability	37
6.3.	Measures to Minimize Bias: Randomization and Blinding	

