4.4. End-of-Study Definition

A participant is considered to have completed the study if he or she has completed all required phases of the study, including the last visit or the last scheduled procedure shown in the SoA (Section 1.3).

The "end of the study" is defined as the date of the last visit or last scheduled procedure shown in the SoA for the last participant in the study globally.

5. Study Population

Prospective approval of protocol deviations to recruitment and enrollment criteria, also known as protocol waivers or exemptions, is not permitted.

All screening evaluations must be completed and reviewed to confirm that potential participants meet all eligibility criteria.

The investigator will maintain a screening log to record details of all participants screened and to confirm eligibility or record reasons for screening failure, as applicable.

For screen failures and rescreening activities within the screening period, see Section 5.4.

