9.2. Sample Size Determination

Approximately 100 patients will be screened to achieve approximately 63 participants randomized in a 2:1 ratio to one of two treatment groups:

approximately 42 participants randomized to LY3041658, and

approximately 21 participants randomized to placebo.

For all randomized patients, approximately 45 patients are expected to complete the 16 weeks' treatment period. This sample size provides at least 80% power to the primary endpoint of HiSCR response. This calculation is a 2-sided test for superiority of LY3041658 compared to placebo on HiSCR response rate with significance level of 0.05 CCl

CCI

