## **6.5. Patient Disposition**

A description of participant disposition will be provided, including a summary of the number and percentage of participants entered into the study, enrolled in the study, and treated, as well as the number and percentage of participants completing the study (participants who receive at least

1 dose of study drug and have at least 1 postbaseline assessment), or discontinuing (overall and by reason for discontinuation). A summary of important protocol deviations will be provided.

[figure not shown]

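### The disposition summary counts anyone with one dose and one post-baseline assessment as completing the study, which contradicts Protocol 4.4, inflates the completion figure and makes completed and discontinued overlap

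*Protocol*

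**What the plan says.** Protocol 4.4 gives the participant-level definition: "A participant is considered to have completed the study if he or she has completed all required phases of the study". The sentence goes on to include the last visit or last scheduled procedure in the Schedule of Activities.

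Protocol 9.4.1.1 plans a summary of numbers and percentages entered, enrolled, treated, completing the study, and discontinuing. A parenthesis after completing the study defines that group as "participants who receive at least 1 dose of study drug and have at least 1 postbaseline assessment". SAP 6.5 carries the same rule ("1 dose of study drug and have at least 1 postbaseline assessment"). In both sections the same sentence continues with the other outcome: "or discontinuing (overall and by reason for discontinuation").

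Three other places bear on the point:

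- Protocol 9.2 uses completion in its ordinary sense for the double-blind period: of about 63 randomized, "approximately 45 patients are expected to complete the 16 weeks" of treatment.
- Protocol 9.5 sets the primary database lock for when every participant has either completed Treatment Period 1 or discontinued. It treats these as alternatives, and SAP 6.12 does likewise.
- The amendment rationale at the front of the protocol says "DSAD discontinuation rate has been higher than expected", and gives this as the reason for raising the screening and enrolment numbers.

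**The concern.** One dose plus one later assessment describes an evaluable participant, not one who finished the study. Someone who stops after the Week 2 visit meets that rule and is also a discontinuation. The two rows of the table would then not be exclusive, and the completion row would say little about how many people stayed.

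This matters more here than in a trial with little dropout. The sponsor has recorded that discontinuation exceeded expectation, and participants who discontinue before Week 16 are scored as nonresponders (Protocol 9.1, SAP 6.1). A reader of the HiSCR result will want to know how much of the nonresponse is failed lesion response and how much is dropout. A completion figure near 100% would be misleading for that purpose.

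**Working it through.** **Step 1: are the definitions compatible?** Protocol 4.4 requires all required phases through the last visit or procedure, which for a participant on the full schedule is Visit 802 at Week 46. Protocol 9.4.1.1 and SAP 6.5 require one dose and one post-baseline assessment. Every dosed participant who meets the first meets the second, but not the reverse. A participant who leaves in between is a completer under one rule and not under the other. Neither text is redacted, and neither belongs to the amendment log.

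**Step 2: how often would they differ?** The Schedule of Activities (Protocol 1.3, Table 1) has lesion counts, patient-reported outcomes, vital signs and laboratory tests from Visit 3 at Week 2. Protocol 7.1 and 7.1.1 require an early termination visit and follow-up visits for anyone who stops study drug early, and Protocol 7.2 asks for an early termination visit, if possible, on withdrawal from the study. Nearly every dosed discontinuer would therefore have a post-baseline assessment. The overlap is the usual case.

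**Step 3: inputs for the size.**

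- Protocol 9.2: 63 randomized (42 + 21), 45 expected to complete 16 weeks.
- SAP 6.2: 51 randomized (34 + 17), 45 expected to complete 16 weeks.
- Assumption: the documents state no rate for completing the whole study, so Week 16 completion stands in for it. Whole-study completion cannot be higher.
- Assumption: k randomized participants have no dose or no post-baseline assessment. The documents do not give k; 0 and 3 are shown.
- Percentages are of participants randomized.

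**Step 4: the plan's expectation.** Completion is 45/N and non-completion is (N − 45)/N.

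- Protocol: 45/63 = 71.4%, leaving 18/63 = 28.6%.
- SAP: 45/51 = 88.2%, leaving 6/51 = 11.8%.

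**Step 5: the disposition rule as written.** Completion is (N − k)/N. The overstatement is that figure minus 45/N. The overlap is (N − k) + (N − 45) − N = N − 45 − k, counting all who miss Week 16 completion as discontinued.

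| N | k | Completion under the rule | Week 16 expectation | Overstatement | In both rows |
|---|---|---|---|---|---|
| 63 | 0 | 63/63 = 100% | 71.4% | 28.6 points | 18 |
| 63 | 3 | 60/63 = 95.2% | 71.4% | 23.8 points | 15 |
| 51 | 0 | 51/51 = 100% | 88.2% | 11.8 points | 6 |

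With N = 63 and k = 0, the completed and discontinued rows would sum to (63 + 18)/63 = 128.6%.

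**Step 6: does the definition enter any analysis?** The mITT and Safety sets need one dose. The Per Protocol Set in SAP 6.3.1 depends on missed doses. Nonresponse for discontinuers and for missing HiSCR is set by Protocol 9.1 and 9.4.1.3 and by SAP 6.1 and 6.4. None refers to completer status.

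**The case against.** A reader might infer that this rule conceals the dropout that prompted the amendment. The documents do not support that. The sentence containing the faulty parenthesis also commits to reporting discontinuations, overall and by reason. SAP 6.3.3 lists discontinuation among the outcomes compared between arms with Fisher's exact test. Discontinuation due to adverse events and duration of exposure are summarized as well (SAP 6.9.2.2 and 6.9.1). The amendment rationale explains the larger enrolment and has no connection with this table.

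A reader might also infer that the primary result is affected. It is not, as Step 6 shows.

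The size can be challenged too. The 45 refers to the 16-week period, whereas the parenthesis concerns the whole study; 100% assumes that every randomized participant is dosed and assessed; and the SAP's own enrolment figure gives a smaller gap. These objections stand, which is why the size is given as a range with its assumptions.

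Finally, a programmer might use the participant disposition form mentioned in Protocol 8.3.1 together with Section 4.4, and ignore the parenthesis. That is possible, but it means departing from what the SAP says. The misreported figure is what follows from applying the text literally.

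The discontinuation row does not fully make up for the error. Neither section splits disposition by treatment period, so a stop at Week 2 and a stop at Week 30 could fall in the same row, and Week 16 completion could not be read from it.

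**Conclusion.** The conflict is certain. Protocol 9.4.1.1 and SAP 6.5 contradict Protocol 4.4. Applied literally, their rule gives an inflated completion percentage and a completed row that overlaps the discontinued row.

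The size is less certain. With Week 16 completion as a proxy, the overstatement is about 24 to 29 points on the protocol's 45 of 63, for 3 or 0 participants without a dose or post-baseline assessment. It is up to about 12 points on the SAP's 45 of 51. Since whole-study completion can be no higher than Week 16 completion, the gap against the Section 4.4 definition could be wider, but the documents give no figure for it.

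The consequence is limited to a descriptive count. Dropout remains visible in the discontinuation rows, and no analysis set, hypothesis test or imputation rule changes. It should be corrected because it is a definite error in a table that readers of a trial with high discontinuation will consult.

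**What to change.** In Protocol 9.4.1.1 and SAP 6.5, delete the parenthesis and refer to the definition in Protocol 4.4, so that a participant is counted as completed or discontinued but never both.

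Preferably, also report completion of Treatment Period 1 (Week 16) by arm, which is the figure needed to read the HiSCR result. Resolving the contradiction does not require this addition, but it needs no new data. It would help to say whether the discontinued row means study drug or study, because Protocol 7.1.1 keeps participants who stop drug in the study for an early termination visit and follow-up.

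If a count of participants with one dose and one post-baseline assessment is wanted, it can stay as a separate row under another label.

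The cost is one sentence in each document and a less favourable completion figure.

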9.4.1.2. Participant Characteristics

Demographic data are collected and reported to demonstrate that the study population represents the target patient population. A summary of baseline participants and disease characteristics, historical diagnoses, pre-existing conditions, and prior therapies will be reported by cohort using descriptive statistics. Other participant baseline characteristics will be summarized by group as deemed appropriate.

9.4.1.3. Missing Data Imputation

Missing data on the primary endpoint, HiSCR response, will be imputed as nonresponse. For other endpoints, including continuous secondary endpoints, missing data may be imputed using the last observation prior to missingness or other appropriate imputation methods.

9.4.2. Primary Endpoint

The primary comparison of interest is the proportion of participants achieving HiSCR response at Week 16. The objective of the primary endpoint is to establish superiority of LY3041658 over placebo (see Section 9.4.1).

The primary endpoint will be analyzed using logistic regression on the mITT population. The treatment difference and 95% CIs will be reported.

9.4.3. Secondary Endpoints

Secondary comparisons of interest are the mean change from baseline to Week 16 for

- total number of abscesses and inflammatory nodules (AN count), and
- Skin Pain HS NRS.

An analysis of covariance (ANCOVA) model will be used for analysis of these secondary endpoints.

9.4.4. Exploratory Endpoints

Exploratory analyses will be further described in the SAP that is finalized before database lock.

9.4.4.1. Patient-Reported Outcomes

Categorical variables will be analyzed using logistic regression analyses, whereas mixed-effects model of repeated measures (MMRM) will be the primary method of analysis for continuous endpoints. The analyses will be based on the mITT population, unless otherwise specified.

9.4.4.2. Pharmacokinetic Analyses

Plasma concentrations of LY3041658 will be listed by time point using descriptive statistics. The data may also be analyzed using a population approach via nonlinear mixed effects modeling (NONMEM) with the NONMEM software. The PK data from Study DSAD may be combined with data from another study in the clinical development program to improve PK parameter estimation.

9.4.4.3. Evaluation of Immunogenicity

Frequencies and percentages will be tabulated for the following:

- participants with pre-existing ADA, and
- participants who are TE-ADA positive (TE-ADA+) to LY3041658.

Treatment-emergent ADAs are defined as those with a titer 2-fold (1 dilution) greater than the minimum required dilution if no ADAs were detected at baseline (treatment-induced ADA) or those with a 4-fold (2 dilutions) increase in titer compared with baseline if ADAs were detected at baseline (treatment-boosted ADA). For the TE-ADA+ participants, the distribution of maximum titers will be described. The frequency of neutralizing antibodies, if assessed, may also be tabulated for the TE-ADA+ participants.

The relationship between the presence of ADA and the LY3041658 concentrations and PD response to LY3041658, including safety and efficacy, may also be assessed. Additional details may be provided in the SAP.

9.4.4.4. Other Exploratory Endpoints

Exploratory efficacy endpoint data, PD data, and biomarker data will be analyzed as described in the SAP. Relationships between LY3041658 exposure and select biomarkers and clinical efficacy endpoints may be explored.

9.4.5. Safety Analyses

Safety analyses will include adverse events, SAEs, AESIs, C-SSRS, vital signs, ECGs, and laboratory analytes, using the Safety Population data descriptively summarized by treatment group. Categorical safety measures will be summarized with incidence rates. Continuous safety measures will be summarized as mean change by visit. Exposure to study intervention will be calculated for each participant and summarized by treatment group.

Adverse events will be coded according to the *Medical Dictionary for Regulatory Activities* (MedDRA) and summarized by system organ class (SOC), preferred term, severity, and

relationship to the study intervention. A treatment-emergent adverse event (TEAE) is defined as an event that first occurred or worsened in severity after baseline, with baseline defined as all pre-existing conditions recorded at Visit 1 and any adverse events recorded before the first dose of study intervention (that is, during the interval between Visits 1 and 2 and recorded with the time of onset before the first dose of study intervention). The treatment periods will be used as the postbaseline period for the analysis. Safety analyses will be conducted separately for each treatment period. For events that are gender specific, the denominator and computation of the percentage will include only participants from the given gender.

The number and percentage of participants who experienced TEAEs, TEAEs by maximum severity, deaths, SAEs, TEAEs related to study intervention, discontinuations from the treatment due to an adverse event, and AESIs will be summarized. Treatment-emergent adverse events (all, by maximum severity), SAEs including deaths, and adverse events that lead to treatment discontinuation will be summarized and analyzed by MedDRA SOC and preferred term.

Treatment-related TEAEs (TEAEs related to study intervention) are defined as events that are indicated by the investigator on the eCRF to be related to treatment.

Adverse events of special interest will be identified by a standardized MedDRA query (SMQ) or a Lilly-defined MedDRA preferred term listing.

Suicide-related thoughts and behaviors occurring during treatment will be summarized based on responses to the C-SSRS consistent with the C-SSRS Scoring and Data Analysis Guide (Columbia Lighthouse Project WWW).

Follow-up emergent adverse events, SAEs including deaths, and adverse events that lead to study discontinuation will be summarized. All adverse events, including pre-existing conditions, will be listed by participant, visit, preferred term, treatment group, severity, and relationship to the treatment.

9.4.6. Other Analyses

Sensitivity Analyses

Fisher's exact test may be used as an alternative to logistic regression on the primary endpoint due to the small sample size for this analysis. Other sensitivity analyses will be considered for the secondary endpoints.

9.5. Interim Analyses

The analysis for the primary database lock will be conducted when all participants have either completed the double-blind treatment period (Treatment Period 1) or have discontinued.

Interim analyses at other time points, including time points prior to the primary database lock, may be conducted using safety and/or efficacy data. These interim analyses will be used to support planning activities associated with the development program and to aid in the development of PK/PD modeling. No adjustment of type I error will be performed.

Unblinding details will be specified in the unblinding plan section of the SAP or in a separate unblinding plan document.

Assessments of unblinded interim data will be conducted by an Internal Assessment Committee (IAC) with a limited number of prespecified team members who do not have direct site contact or data entry or data validation responsibilities (see Appendix 10.1, Section 10.1.5). Only the IAC will be authorized to evaluate unblinded interim efficacy and safety analyses.

To minimize bias, the SAP and PK/PD analysis plan will be finalized and approved before any unblinding. Information that may unblind the study during the analyses will not be reported to study sites or the blinded study team until the study has been unblinded.

Study sites will receive information about interim analysis results only if the investigators need to know for the safety of their participants.

The SAP will describe the planned interim analyses in greater detail.

9.6. Data Monitoring Committee (DMC)

Not applicable. An IAC will be used to conduct the interim analysis (see Section 9.5 and Appendix 10.1, Section 10.1.5).

10. Supporting Documentation and Operational Considerations

10.1. Appendix 1: Regulatory, Ethical, and Study Oversight Considerations

10.1.1. Regulatory and Ethical Considerations

This study will be conducted in accordance with the protocol and with the following:

- Consensus ethical principles derived from international guidelines, including the Declaration of Helsinki and Council for International Organizations of Medical Sciences (CIOMS) International Ethical Guidelines
- Applicable International Council for Harmonisation (ICH) Good Clinical Practice (GCP) Guidelines, and
- Applicable laws and regulations.

The protocol, protocol amendments and addenda, ICF, IB, and other relevant documents (for example, advertisements) must be submitted to an IRB/IEC by the investigator and reviewed and approved by the IRB/IEC before the study is initiated.

Any amendments to the protocol will require IRB/IEC approval before implementation of changes made to the study design, except for changes necessary to eliminate an immediate hazard to study participants.

The investigator will be responsible for the following:

- Providing written summaries of the status of the study to the IRB/IEC annually or more frequently in accordance with the requirements, policies, and procedures established by the IRB/IEC
- Notifying the IRB/IEC of SAEs or other significant safety findings as required by IRB/IEC procedures, and
- Providing oversight of the conduct of the study at the site and adherence to requirements of 21 United States Code of Federal Regulations (CFR), ICH guidelines, the IRB/IEC, European regulation 536/2014 for clinical studies (if applicable), and all other applicable local regulations.
- After reading the protocol, each principal investigator will sign the separate protocol signature page and send a copy of the signed page to a Lilly representative.

Investigator sites are compensated for participation in the study as detailed in the clinical trial agreement.

10.1.2. Financial Disclosure

Investigators and subinvestigators will provide the sponsor with sufficient, accurate financial information as requested to allow the sponsor to submit complete and accurate financial certification or disclosure statements to the appropriate regulatory authorities. Investigators are responsible for providing information on financial interests during the course of the study and for 1 year after completion of the study.

